6.0 STATISTICAL PROCEDURES

6.1 Statistical Analysis Plan

Given the size of this initial IND study and the lack of statistical power, descriptive statistic will be used to report the results. A formal statistical plan for the study analyses will be prepared before the treatment portion of the study is completed.

6.1.1 STUDY POPULATIONS

The intent-to-treat (ITT) population will include all randomized subjects. All efficacy analyses will be based on this population.

The safety population will include all subjects who have been received at least one dose of L1-79 or placebo. If all subjects are treated, this population will be identical to the ITT population.

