APPENDIX E: SAMPLE COLLECTION METHODS.....		58
APPENDIX F: DSM-5 DIAGNOSTIC CRITERIA FOR AUTISM SPECTRUM DISORDER		59

RESTRICTED DISTRIBUTION OF PROTOCOLS

- This protocol contains information that is confidential and proprietary. The information contained herein is provided for the purpose of conducting a clinical trial in collaboration with [name].
-
- The contents of this protocol may be disclosed to study personnel under your supervision and to your Institutional Review Board(s). The contents of this protocol may not be disclosed to any other parties (unless such disclosure is requested by [name]).

PROTOCOL SYNOPSIS

- Study Drug: L1-79
- Protocol Number: HT 02-121

Protocol Title: A Phase 2 Safety Study of L1-79 in the Treatment of Autism

- Study Phase: 2
- **Study Design:** This study has a dose escalating cohort design. Treatment arms consist of L1-79 at doses of 100 mg t.i.d (or placebo), or 200 mg t.i.d., (or placebo). Pharmacokinetics will be assessed in initial cohorts of 5 patients for each dose group followed by a double blinded, placebo-controlled assessment of PK/PD and safety in a cohort of 15 patients randomized 2:1 active to placebo. Groups 1& 2 below can start simultaneously. While the FDA is reviewing the data from Group 1, Groups 2 and the placebo patients randomized with Group 2 will be ongoing. All 5 subjects assigned to Group 1 (100 mg L1-79) must have completed the PK portion of the study with results analyzed and accepted by the FDA before subjects in Groups 3-5 can begin treatment.
- Sample Size: N=40
 - Group 1 (n=5) 100 mg L1-79 (1x100mg capsule+1 placebo capsule)
 - Group 2 (n=10) 100mg L1-79 (1x100mg capsule+1 placebo capsule)
 - Group 3 (n=5) 200 mg L1-79 (2x100 mg capsules)
 - Group 4 (n=10) 200 mg L1-79 (2x100 mg capsules)
 - Group 5 (n=10) Placebo (2 placebo capsules)

All Groups will receive the assigned study drug three-times daily.

- **Study Population:** Male subjects with autism between the ages of 13 and 21 years of age who meet the entry criteria and who are able to complete standardized measures allowing them to participate in this study.

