5.1.3 RANDOMIZED GROUP

Following the enrollment of 5 open label patients as described in the Assigned Dosage Groups, an additional 15 patients at each dose level will be randomized 2:1 to receive either active drug or placebo (2 active to each placebo patient. These patients will be treated identically to those in the Assigned Dosage Groups with 3 exceptions:

1. No pharmacokinetic samples will be drawn,
2. No EKG will be performed
3. They will not have the 1 week follow-up, just the 1 month follow up.

After being randomized to a treatment arm each patient will be assigned a study number comprised of a 2-digit site identifier and a 3-digit patient identifier as described above.

Study numbers will not be assigned until a patient is qualified and entered into the trial. Screening failures will not be assigned numbers. However, a list of screen failures and their demographic data will be maintained by the Investigator.

Patients will be enrolled and receive their first dose within 3 weeks of completing the screening procedure.

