5.10 Discontinuation of Study Subjects

A patient may be discontinued for the following reasons:

- Non-compliance with treatment regimen or follow up requirements
- Lost to follow-up
- Patient and/or care giver requests voluntary withdrawal
- Adverse event sufficient in the opinion of the Investigator to warrant cessation of treatment
- Adverse event requiring unblinding of the patient's assigned treatment
- Investigator decision

Discontinuation for any reason will be documented in the eCRF and supporting documentation will be added to the patient file. Appropriate treatment will be provided for any disease or syndrome.

All subjects who receive a single dose, irrespective of discontinuation, will be followed for a period of 4 weeks subsequent to the first dose in order to determine whether the treatment was safe.

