5.13 Study Discontinuation Criteria

The occurrence of a grade 3 or 4 AE in any patient will result in the immediate discontinuation from this study. In the event of a grade 2 AE, the Investigator, at their discretion, may withhold treatment until the event resolves to grade 1 or less.

The Sponsor may at its discretion terminate the study as a whole if conditions warrant this action. The study site Investigator bears responsibility for orderly discontinuation of the study subjects enrolled at his/her study site.

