5.14 Dose Adjustment and Stopping Rules

As this is a double-blind trial and the doses administered to a given patient are not known to the Investigator or the sponsor. In the event a grade 1 or 2 adverse event occurs, the regimen will be paused until a resolution of the event occurs and the Investigator feels it is safe to continue. Should the Investigator feel it is not safe to continue, or should the event reoccur that patient will be terminated from this trial and appropriate therapeutic measures taken. Any dosing hiatus or discontinuation will be noted in the case report form.

In the event a patient experiences a grade 3 (Severe) or 4 (Life Threatening) adverse event medication will be discontinued immediately and will not resume until the Investigator and the DMC have agreed that it is safe to do so.

In the event of two grade 3 (Severe) or 4 (Life Threatening) adverse events as found in the schedule of adverse events presented in [Appendix A](#), the study at any site will be stopped until such time as the Principal Investigator, Co-Investigator at that site and the Sponsor have determined appropriate measures to assure the safety of future subjects.

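### Efficacy is to be analysed in all randomised patients, but no section requires efficacy ratings after a patient is taken out of the study or says how missing Week 4 values are handled

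*Combined protocol and SAP*

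**What the plan says.** **Analysis set.** Section 6.1.1: "The intent-to-treat (ITT) population will include all randomized subjects. All efficacy analyses will be based on this population". Section 6.1.5.1 makes change in CGI the main efficacy endpoint, without a time point, and promises comparisons of the active arms with each other and with placebo. Section 6.1 adds: "Given the size of this initial IND study and the lack of statistical power, descriptive statistic will be used to report the results". It leaves a formal statistical plan to be written before treatment ends.

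**Exit from the study.**
- Section 5.13: "The occurrence of a grade 3 or 4 AE in any patient will result in the immediate discontinuation from this study".
- Section 5.14, on grade 1 or 2 events: drug is paused at first; if continuing is judged unsafe, or "should the event reoccur that patient will be terminated from this trial", participation ends.
- Section 5.14, on grade 3 or 4 events: "medication will be discontinued immediately and will not resume until the Investigator and the DMC have agreed that it is safe to do so".
- Section 5.10 lists reasons for which a patient may be discontinued, among them an adverse event, unblinding, Investigator decision and "Non-compliance with treatment regimen or follow up requirements".

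**After exit.** Section 5.10 follows everyone who took a dose for 4 weeks counted from the first dose and gives safety as the purpose. It names no assessments.

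**Rating schedule.** Appendix A has CGI-S, CGI-I, ABC-C, SRS and RBS-R at Weeks 1 to 4. ADOS is at screening and Week 4 only, and VABS II is at baseline, Week 4 and the follow-up visits. Section 5.8 ties CGI-I to the weekly treatment visits. Section 5.9.2.6 puts ADOS in the final dosing week, with the patient still taking drug.

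**The concern.** An intention-to-treat set is only as good as the outcomes collected in it. Here the set is defined by randomisation, but collection of outcomes appears to end when a patient leaves, and several exits are triggered by adverse events. If such events are commoner on L1-79, the active-arm patients who still have a Week 4 rating are a selected group that tolerated the drug, compared with a less selected placebo group. The main rating is the Investigator's own judgement, and the report would carry the ITT label.

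The efficacy picture has consequences even though it is secondary. Clinical usefulness is part of the purpose in section 2.1, and sections 5.1.4 and 5.9.4 make further treatment depend partly on perceived benefit.

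**Working it through.** **1. Numbers in the plan.** The synopsis gives "Sample Size: N=40". The group sizes sum to it: 5 + 10 + 5 + 10 + 10 = 40. Section 5.1.3 says "an additional 15 patients at each dose level will be randomized 2:1 to receive either active drug or placebo", which is 10 active and 5 placebo per dose level. The randomised set is therefore 10 + 10 + 10 = 30: two active arms of 10, and 10 placebo patients. The plan gives no alpha, effect size, SD or power, so there is no power figure to reproduce.

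**2. What an early leaver has.** Take a patient who leaves after the Week 1 visit.

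| Instrument | Post-baseline data before exit | Week 4 value |
|---|---|---|
| CGI-S, CGI-I, ABC-C, SRS, RBS-R | Week 1 | Not required by any section |
| VABS II (Appendix A) | None | Not required by any section |
| ADOS | None | Not required; 5.9.2.6 expects the patient to be on drug |

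Appendix A has no early-termination column. Section 5.9.1.4.2 allows the second ADOS up to 1 week after the last dose, which does not match 5.9.2.6 and does not provide a Week 4 value for someone who stops in Week 1. The follow-up in 5.10 runs to about Day 28, so it reaches the Week 4 visit (Day 28 ± 2).

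**3. Effect on an arm mean.** Let k of 10 patients be missing at Week 4, and let g be the gap between what they would have scored and the mean of those who remain.

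Observed-case mean minus all-randomised mean = −(k/10) × g, so its size is (k/10) × g.

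The gap is not in the documents. I assume 2 CGI-I points, range 1 to 3.
- k = 1: 0.1 × 2 = 0.2 (0.1 to 0.3)
- k = 2: 0.2 × 2 = 0.4 (0.2 to 0.6)

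The same formula applies to placebo. A lost placebo patient with the same gap moves the comparison the other way, by 0.1 to 0.3 if the 10 placebo patients are pooled, or (1/5) × g = 0.2 to 0.6 if each cohort's 5 are kept separate. The net direction depends on which arm loses more.

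**4. Effect on a responder rate.** Let r of 10 respond and let k non-responders be lost. The all-randomised rate is r/10 and the observed-case rate is r/(10 − k). The values of r and k are assumed.

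| r | k = 1 | k = 2 | k = 3 |
|---|---|---|---|
| 3 (30%) | 33.3% | 37.5% | 42.9% |
| 4 (40%) | 44.4% | 50.0% | 57.1% |
| 5 (50%) | 55.6% | 62.5% | 71.4% |

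The inflation runs from 3.3 to 21.4 percentage points.

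**5. How likely is any loss?** The plan assumes no dropout rate. Section 7.2.2 packs drug for 12 per group to cover 2 dropouts, and 2/12 = 16.7%; that is a supply allowance, not a forecast. With 20 randomised active patients, P(at least one loss) = 1 − (1 − d)^20:
- d = 5%: 64%
- d = 10%: 88%
- d = 16.7%: 97%
- d = 25%: 99.7%

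**The case against.** The strongest reply is that the documents contain no completer analysis. A reader might infer that the ITT analysis cannot be done, that it turns into a completer analysis by rule, or that everyone who stops drug is put out with safety contact only. The text supports none of these:

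- Section 6.1.1 says the opposite of a completer restriction.
- The main endpoint has no fixed time point, 6.1.5.2 describes scores over time, and five instruments, including the CGI, are rated weekly. A patient who leaves after Week 1 can still appear in an ITT summary over time.
- Stopping drug is not always leaving. A first grade 1 or 2 event only pauses drug under 5.14, and 5.14 allows resumption after a grade 3 or 4 event.
- Section 5.10 gives a safety purpose but does not forbid ratings. The Week 8 visit, under a heading that covers all patients, includes most of the scales. Whether discontinued patients attend it is unclear.
- Section 6.1.3 already summarises reasons for discontinuation.
- Safety is the primary objective, efficacy is descriptive, and the formal statistical plan is still to come.
- The exit rules apply to placebo patients too, so neither the direction nor the size of any bias is established.

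All of this stands, and it limits the point. It does not remove it. A later statistical plan can choose a missing-data method but cannot create Week 4 ratings that were never made, and carrying forward or modelling earlier scores would be imputation for which no rule is given. Descriptive status is limited comfort: with no test, readers will rely on the arm summaries and their label.

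**Conclusion.** The point holds in this form: the plan names an all-randomised efficacy set but requires no efficacy ratings after a patient leaves and gives no missing-data rule, while several exits are driven by adverse events. Week 4 summaries would probably be observed-case and may favour patients who tolerate the drug. The gap is clearest for ADOS and VABS II.

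The size is illustrative. A shift of 0.1 to 0.3 CGI-I points per lost patient in an arm of 10 rests on an assumed gap of 1 to 3 points; the 3.3 to 21.4 point responder inflation rests on assumed counts. A lean towards L1-79 further assumes that more active than placebo patients leave.

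Separately, 5.13 and 5.14 disagree on whether a grade 3 or 4 event ends study participation or only interrupts medication. Until they are reconciled, it is unclear which patients go on to be rated.

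This should be fixed. It is not critical, because efficacy is secondary and descriptive and no error rate or sample size depends on it.

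**What to change.** 1. In 5.10, 5.13 and 5.14, separate stopping study drug from leaving the study. Leave unchanged the rules on when drug is stopped.
2. Within the 4-week follow-up that 5.10 already promises, keep the scheduled Week 1 to 4 visits for efficacy ratings in every randomised patient unless consent is withdrawn: CGI-S, CGI-I, ABC-C, SRS and RBS-R weekly, VABS II and ADOS at Week 4. Section 5.10 does not say that its contacts are weekly, so this must be written in.
3. Amend the on-medication wording for ADOS in 5.9.2.6 to match.
4. In 6.1.1, state that ITT summaries use these values regardless of drug discontinuation (a treatment-policy approach), and add a simple sensitivity summary for values still missing after loss to follow-up or withdrawn consent.
5. Present the discontinuation reasons in 6.1.3 by arm.
6. The sponsor must reconcile 5.13 with 5.14 on grade 3 or 4 events. This review takes no position on which rule should apply.

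The cost is an amendment and some extra visits and existing rating forms for the patients who stop. The downsides are a modest burden on families who have stopped drug and possibly a smaller apparent effect. The change has to be made before patients leave, because the ratings cannot be recovered afterwards.

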6.1.2 CHARACTERIZATION OF THE STUDY POPULATION

Distributions of the following data will be described by treatment group.

Baseline data:

- Demographics
- Medical history
- Psychometric test scores
- Physical examination parameters
- Vital signs
- ECGs
- Safety labs including hematology and serum chemistry

6.1.3 STUDY CONDUCT

Disposition of all subjects in the study will be summarized including the number of subjects who completed the study as well as the reason for discontinuation for non-completers. The number of subjects in each of the analysis populations, the duration of time on study, and the number of injections will also be displayed. The number and type of protocol violations will be summarized

6.1.4 SAFETY

Adverse events will be coded using MedDRA and will be presented by body system and preferred term. Concomitant medications will be coded using [concomitant medication coding dictionary] and summarized by drug class and generic name.

Tables and graphs will show changes from baseline through 8 weeks of treatment and 26 weeks of follow-up in:

- Physical examination

- Vital signs
- Safety labs, including hematology and serum chemistry
- Cardiovascular changes, including orthostatic blood pressure.
- EKG changes from in the Assigned Dosage Group patients

Other safety data that will be presented include:

- Dose limiting toxicity
- Adverse events along with their severity and potential relationship to study treatment.
- Concomitant medications

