3.2 Study Endpoints

3.2.1 SAFETY ENDPOINTS

Safety is the primary endpoint and analysis will focus on the following endpoints at each time point from the start of dosing through the 4-week treatment and observation period, and at a 4-week follow-up visit:

- EKG
 - Patients in the Assigned Dosage Groups (1 and 3) will also have an EKG at baseline and within 3 days prior to the their visits as described in [5.1.2](#).
 - In the event any EKG abnormalities appear to result from treatment in the Assigned Dosage Group then additional EKG may be required as described in section [5.5.2](#)
- Before and after the Active Treatment phase
 - Physical exam with vital signs, including orthostatic blood pressure
 - Hematology
 - Serum Chemistry
 - Urinalysis
- Active Visits, weeks 1-4
 - Vital signs findings, including orthostatic blood pressure,
 - Adverse Event (AE) reporting
 - Assessment of concomitant medications

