5.1.4 PLACEBO ROLLOVER TO ACTIVE

- If the Investigator in collaboration with Yamo Pharmaceuticals (the manufacturer of the drug) believes that the L1-79 is sufficiently well tolerated and clinically useful to warrant continued treatment, then patients receiving placebo will be eligible for a 4 week course of treatment with L1-79 as outlined for the other patients treated with active drug in this protocol. At the present time, the permitted course of therapy does not extend past 4 weeks.
- The random code will only be broken after the last patient in a group has completed the last scheduled follow-up visit.
- Placebo treated patients who qualify for active treatment in a rollover fashion, and who desire to do so, will be indicated in the eCRF as having affirmatively requested active treatment under the protocol. They will then qualify for extended treatment with active medication under the existing protocol and new, active, medication will be assigned to them on an open label basis at the same dose as their group had been receiving.
- Placebo rollover patients will be seen at 3 scheduled visits plus a follow-up visit as described in [Appendix B](#).
 - There will be no Screening, as patients have already been screened
 - Rollover patients will not have any PK tests conducted
 - Baseline Visit
 - No randomization is required.
 - Roll over patients will get a physical (including vital signs)
 - Blood and urine samples will be taken for hematology, urinalysis and serum chemistry assessments.
 - No retained samples to be collected
 - All psychometric assessments described in [Appendix A](#) for the baseline visit will be taken
 - The initial 2 weeks of doses of active medication will be dispensed.
 - Week 2
 - A physical examination will be performed and the parents interviewed as to their observations regarding the effects of treatment over the past two weeks, and the final two weeks of active medication doses will be dispensed.
 - Patients will get a physical (including vital signs)

- No blood or urine samples will be taken
- No psychometric tests will be conducted at this visit.
- Week 4
 - The final active treatment assessment will be made, which will include a physical examination,
 - All blood and urine analysis described previously
 - No retained samples to be collected
 - All psychometric tests described for the 4 week visit in [Appendix A](#).
 - Patients will get a physical (including vital signs)
 - A week 4 ADOS will be taken

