5.2 Drug Administration

5.2.1 THE L1-79 REGIMEN

Subjects will receive either 100 mg or 200 mg or matching placebo t.i.d. for a total of 28 days of dosing. The doses of L1-79 were determined based upon preliminary clinical research in subjects between 2½ and 24 years of age and doses between 90 and 200 mg t.i.d..

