5.9.2.8 Week 8 Follow-Up Visit (Study Day 56)

All patients are to receive:

- Physical exam with vital signs
- Hematology
- Urinalysis
- Serum chemistry
- Blood draw for storage
- ASD assessments will be performed, including: ABC, SRS, RBS-R, CGI-S SAS, VAB II, and CGI-I
- Record all adverse events
- Physical exam with vital signs
 - Question caregiver or patient about the patient's week, including questions regarding any changes in home life activities, events at school, sleep, or other matters germane to an understanding of the patient's autistic
 - Record concomitant medications

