APPENDIX B: STUDY PLAN ACTIVE PLACEBO ROLLOVER PHASE

Form Name	Visit			
	wk 0 Baseline	Wk 2	Wk 4	4 wk FUP
Study Day	0 ± 2	14 ± 2	28 ± 2	56 ± 2
Date	x	x	x	x
Lab - Hematology	x		x	x
Lab- Serum Chemistry	x		x	x
Urine Analysis	x		x	x
Vital Signs	x	x	x	x
Physical Examination	x	x	x	x
ADOS			x	
SAS	x			x
VABS II	x		x	x
ABC-C (all scales)	x		x	x
SRS	x		x	x
RBS-R	x		x	x
CGI-S	x		x	x
CGI-I			x	x
CGI-Overall score	x		x	x
Study Drug dispensing	x	x		
Study Drug Administration	x	x	x	
Drug Accountability		x	x	
Adverse Event	x	x	x	x
Prior and Concomitant Medication	x	x	x	x

APPENDIX C: SUBJECT CONSENT FORM**A Phase 2 Safety Study of L1-79 in the Treatment of Autism****Protocol Version: 48****Protocol HT 02-121****Sponsor- [name].**

«PI_FIRST_NAME» «PI_LAST_NAME»
«PHONE_NUMBER»

Invitation to Participate

Your child is being asked to take part in a research study. Before you decide whether or not your child may take part, it is important for you to understand why the research study is being done and to understand its possible risks and benefits in order to make an informed decision. This process is known as informed consent.

As the parent or legal guardian of a study participant that is not legally permitted to consent to be in a research study on his/her own behalf, it is necessary that you sign this Informed Consent Form.. If there will be a caregiver assisting the child, then the caregiver must sign the Study Compliance Agreement provided separately.

This form gives detailed information about the research study that your study doctor will discuss with you. Once you understand this study, you will be asked to sign this form if you wish your child to participate.

There will be no costs to you for your child's participation in the research study. The Sponsor will cover the costs of the study medication and all study related procedures. If your child's caused injury that is confirmed to be due to his/her participation in the study, the Sponsor will cover all the procedures and/or medications in accordance with the Law.

This study is conducted under an approved FDA Investigation New Drug application. Please read the following information carefully and ask the study doctor listed above for more information if anything is not clear.

Introduction

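### The safety window in 6.1.4 (8 weeks of treatment, 26 of follow-up) contradicts the 28-day course and Day 56 last visit, and Section 6 has no rule for placebo patients' open-label rollover data

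*Combined protocol and SAP*

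**What the plan says.** Section 6.1.4 sets the period for the safety displays: "Tables and graphs will show changes from baseline through 8 weeks of treatment and 26 weeks of follow-up in" physical examination, vital signs, laboratory tests, cardiovascular measures and EKG. It is the only safety window in Section 6. The adverse event item lower in the same section has no window.

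The sections that define the endpoint, the dosing and the visits say something else:

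- 3.2.1, which makes safety the primary endpoint, runs "from the start of dosing through the 4-week treatment and observation period, and at a 4-week follow-up visit".
- 5.2.1 gives active drug or "matching placebo t.i.d. for a total of 28 days of dosing".
- 5.1.4 adds that "the permitted course of therapy does not extend past 4 weeks".
- The last visit, in 5.9.2.8 and Appendix A, is the "Week 8 Follow-Up Visit (Study Day 56").

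Section 5.1.4 also lets placebo patients take a 4-week open-label course of L1-79 at their cohort's dose. The schedule is in "APPENDIX B: STUDY PLAN ACTIVE PLACEBO ROLLOVER PHASE", with a new Day 0 and a new Day 56 and with laboratory tests, vital signs, examinations and adverse events recorded. Section 6 never mentions this phase. The safety population in 6.1.1 is anyone who took a dose of L1-79 or placebo, and nothing is said about a patient who took both.

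Two timing statements also matter. Section 6.1: "A formal statistical plan for the study analyses will be prepared before the treatment portion of the study is completed". Section 5.1.4: "The random code will only be broken after the last patient in a group has completed the last scheduled follow-up visit".

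**The concern.** Safety is the primary endpoint, and the 10 placebo patients (5 per cohort) are its only control. The sentence that fixes the reporting period fits no patient's schedule. A window of 34 weeks from baseline is also long enough to take in the rollover phase, during which the same patients receive L1-79. A programmer following 6.1.4 has no instruction on whether those data are left out, shown separately or listed under the randomised arm, nor on which of the two baselines applies. A programmer following 3.2.1 would stop at the follow-up visit. The two sections therefore permit different tables.

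The formal plan is the natural place to settle this. Its deadline is tied to the end of treatment and not to unblinding, so the choice could be made after the first cohort's allocation, including which 5 patients had placebo, is known.

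**Working it through.** **1. Can 8 + 26 weeks be reproduced?** Inputs: 28 days of dosing (5.2.1), last visit at Day 56 (5.9.2.8; ±2 days in Appendix A), up to 3 weeks from screening to first dose (5.1.1), 36 weeks for the whole study (synopsis).

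| Reading | Treatment | Follow-up | Total |
|---|---|---|---|
| 6.1.4 as written | 8 weeks | 26 weeks | 34 weeks (238 days) |
| One patient, blinded phase | 28/7 = 4 | (56 − 28)/7 = 4 | 8 weeks |
| Placebo and rollover phases added | 4 + 4 = 8 | 4 + 4 = 8 | 16 weeks |
| Synopsis study calendar | 8 | 8 | 8 + 8 + 8 + 8 = 32 weeks with recruitment and screening (36 stated) |

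No reading gives 26 weeks of follow-up. A 34-week window plus 3 weeks of screening is 37 weeks for one patient, longer than the 36 weeks given for the entire study.

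**2. What could the extra weeks contain?** Appendix A has no visit after Day 56. The code is held until the group's last follow-up visit, so rollover ordinarily starts no earlier than the patient's own Day 56. On that patient's original clock, the earliest rollover has its last dose at 56 + 28 = Day 84 and its last visit at 56 + 56 = Day 112. A rollover begun by Day 238 − 56 = 182 lies wholly inside the 6.1.4 window. All of it, from the first rollover dose on, lies outside the 3.2.1 window.

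**3. How many patients?** Each cohort randomises 15 patients 2:1, giving 5 on placebo, so 10 in total. Between 0 and 10 could roll over. The documents give no expected number.

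**4. Plan deadline against code break.** Read "group" in 5.1.4 as the dose cohort. This is the likelier reading, because rollover patients receive the dose of the group they came from, and placebo as a numbered group has no dose. Let L1 and L2 be the days on which the last 100 mg cohort patient and the last 200 mg cohort patient start.

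- 100 mg code break: L1 + 56.
- End of blinded 200 mg dosing: L2 + 28.
- The break comes first when L1 + 56 < L2 + 28, that is, when L2 − L1 > 28 days.

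A gap of 28 days puts the two on the same day. A gap of 42 days puts the break 14 days earlier, and a gap of 84 days puts it 56 days earlier. The gaps are illustrations, since no dates are given. The synopsis allows 8 weeks to treat all patients. If that held, the gap could be at most 56 − 28 = 28 days and the break would not come first. Against that, 200 mg enrolment must wait for FDA acceptance of the 100 mg data (3.1).

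If rollover dosing counts as part of the treatment portion, the deadline falls after the 100 mg code break whenever anyone rolls over.

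**The case against.** **The window is leftover text.** This is probably right: 6.1.3 counts injections for an oral capsule, and 6.1.4 contains an unfilled coding-dictionary placeholder. It explains the error without correcting it, and this is still the only window given for the primary-endpoint tables. The objection does stand to this extent: the wrong numbers alone add no blinded-phase data.

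**Nothing tells anyone to pool.** This stands. A reader might infer that the plan counts L1-79 rollover data as placebo data and so shrinks, or for adverse events even reverses, the contrast between L1-79 and placebo. The documents do not support that. Rollover is open label, has its own appendix and has its own Day 0. In a by-visit display the blinded Week 4 contrast is unchanged however many patients roll over. Figures for the shrinkage can be produced. For example, averaging the one blinded and the one rollover on-treatment laboratory visit leaves 1/(1 + f) of the contrast, from all of it at f = 0 to half at f = 1, where f is the share rolling over. That assumes a pooled mean the plan nowhere describes, an equal drug effect in both phases and a value of f the documents do not give. Reversal of an event-rate difference needs assumed event rates as well.

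**Rollover may not happen.** It requires a joint judgement that the drug is tolerated and useful, and a request from the patient. Section 5.9.4 also speaks of considering an amendment to supply open-label drug to placebo recipients. So f = 0 is a real possibility. Even so, 5.1.4 and Appendix B already set out a complete rollover phase, and the analysis section should cover it.

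**The deadline problem is conditional.** This also stands. A reader might infer that the plan will be written after unblinding, but the text only allows it. If the code were held until all of the placebo group across both cohorts had finished, and rollover were not counted as treatment, the plan would ordinarily be due before the break. The appendix titles favour keeping rollover separate from the treatment phase.

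**Conclusion.** Two things are certain from the text: the 6.1.4 window contradicts 3.2.1, 5.1.4, 5.2.1, 5.9.2.8 and Appendix A (34 weeks stated, 8 scheduled), and Section 6 has no rule for rollover data. Together they leave the primary-endpoint tables open to more than one construction.

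The effect on results is nil if nobody rolls over or if the phases are displayed separately. If rollover data from up to 10 patients were listed under placebo, the safety contrast would be blurred by an amount that cannot be estimated from the documents. No error-rate question arises, because 6.1 makes the analysis descriptive.

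The deadline point is weaker. It rests on "group" meaning the dose cohort, and on either a gap of more than 28 days between the cohorts' last starts or rollover dosing counting as treatment. It supports a safeguard and is not a finding of bias. The correction should be made; it is more than clerical because it settles which data the control column contains.

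**What to change.** In 6.1.4, replace the window with wording such as:

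*From baseline through 4 weeks of treatment and the Day 56 follow-up visit. Placebo-column data, including adverse events, end at the Day 56 visit, or at the first rollover dose if that is earlier. Rollover data (5.1.4, Appendix B) are shown in a separate open-label column, with change measured from the rollover baseline.*

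The clause on the first rollover dose will seldom apply, given when the code is broken, but it covers early unblinding. Correcting the window alone is not enough: the rollover schedule has its own Day 0 and Day 56, so a bare reference to Day 56 could be read on either clock.

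In 6.1, replace the deadline with: *signed before the first code break under 5.1.4.*

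The cost is one corrected window and two sentences in 6.1.4, and one clause in 6.1. No patients, visits or data are added.
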